Key elements of the informed consent procedure that are explained to participants for both study aims include: (1) the research status of the study; (2) the confidentiality of the participant's responses; (3) the voluntary nature of the study; and (4) the freedom to withdraw from the study or refuse to answer specific questions at any time. All participants who consent will be provided with a copy of the informed consent form and may contact with the research staff as needed with any questions/concerns.

D.2.b Protections Against Risk

Planned strategies for minimizing potential risks are described in detail below.

- a) **Risk:** Confidentiality and loss of privacy.

Minimization: The risk of inappropriate disclosure of the participant's identity or sensitive data is appropriately minimized. We will make every effort to inform participants about the steps we are taking to ensure the confidentiality and privacy of their responses. In order to protect confidentiality, data will be securely stored and protected as described below.

For Aim 1, participants will have the option of completing the inventories via a secure website (Qualtrics.com) using a unique login ID or password hosted by our Survey Methods Core. Qualtrics, an online data collection website, has SAS 70 Certification and meets rigorous privacy standards. All Qualtrics accounts are hidden behind passwords and all data is protected with real-time data replication (see <https://www.qualtrics.com/security-statement/> for additional information).

For Aim 2, participants will be audio recorded. Once the interviews are recorded, they will be transcribed verbatim by a study team member. Each transcript will be reviewed for accuracy by a second, independent study team member, after which the audio recordings will be destroyed. Audio recordings of interviews will not be used for educational or training purposes.

Data collected at MCC will be maintained at MCC, and data collected at LCCC will be maintained at LCCC. Data sharing will take place as described in section D.3 below. For all aims, physical study data will be kept in locked storage with access restricted to approved study personnel. All electronic data will be uploaded to a secure Access database on a password-protected terminal and server. Only key research personnel will have password access to electronic study data. Participants will be assigned a subject number (001, 002, etc.) that is unique to the study in question, and all data will be stored under that subject number. Participants are only identified by their subject numbers in data analyses/publications. One master list of subject names and corresponding subject numbers will be kept electronically. Only the study coordinator and key research personnel will have access to this list. The list will be password protected and stored on a password protected server that is firewall protected. All research data will remain separate from the master list and identifiers. De-identified data will be kept on file for at least 5 years from the time the IRB accepts the final review and closes the study. At the end of the 5th year of study closure, the de-identified data will be deleted.

- b) **Risk:** Psychological distress, embarrassment, or discomfort.

Minimization: In conducting self-report assessments and interviews, we make every effort to obtain data in a humane, effective, and professional manner. The questions to be employed are standardized and have been used extensively and successfully in prior research. Participants will be informed that they can omit answers to any questions that make them feel uncomfortable without consequence. Participants will be told that they may discontinue a single assessment or participation in the study at any time. Contact information for the site principal investigators (PIs) is provided should participants

have any questions or concerns. Of note, the PIs have extensive experience in collaborative clinical research with human subjects related to cancer and cancer risk. Thus, the PIs have experience managing participant discomfort in the rare situations it arises.

Finally, we note that all members of the research team and personnel involved in recruitment will complete and maintain the necessary Human Subjects and HIPAA Training (e.g. CITI Courses), and copies of these certifications will be kept on file with the site PI.

D.3 Data Sharing

Data elements outlined in this protocol will be exchanged between MCC and LCCC. The following collaborators at Georgetown University Lombardi Cancer Center will have access to MCC data:

[name]
Assistant Professor of Oncology
Member, Cancer Prevention and Control Program

Only de-identified data will be shared via secure file sharing service (ShareFile). Elements of dates will be shared; however, outside collaborators will not have access to our EMR system that would allow for direct identification of patients/participants. A data sharing agreement between Moffitt Cancer Center and Georgetown University Lombardi Cancer Center will be established through Moffitt's legal office.

D.4 Potential Benefits of the Proposed Research to Research Participants and Others

Participants will not directly benefit as a result of taking part in this study, and no guarantee of personal benefit based on study participation will be made to participants. The benefits to society could include a better understanding of the predictors of breast MRI utilization in the high risk population.

The potential risks of this study are not estimated to be over or above stresses encountered in everyday life. The main benefit to participants is involvement in research that may lead to the development of interventions to increase screening breast MRI among future high risk women. In sum, the risks to participants in this study are reasonable in relation to anticipated benefits.

D.5 Importance of the Knowledge to be Gained

Ultimately, we expect this research to lead to the design and development of interventions to increase screening breast MRI among high risk women. Such approaches have the potential to improve guideline concordant care, BC early detection, and BC treatment outcomes. The development and dissemination of efficacious education and intervention materials will offer a significant benefit to at-risk populations as well as the practitioners who treat them.

E. Future Research.

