This multisite study seeks to develop an explanatory framework for breast MRI utilization to inform future interventions. The Health Services Utilization Model (HSUM)²¹ will guide the selection of specific patient-level factors for examination, including predisposing characteristics (knowledge, health/cultural beliefs), enabling resources (social support, cost/insurance coverage), and perceived need (perceived susceptibility, provider recommendation). Using a mixed methods approach, the aims of this study are to:

Aim 1: Assess HSUM factors influencing screening breast MRI utilization in a community-based sample (N=300). Approach: Women with high ($\geq 20\%$) lifetime BC risk (N=300) will be recruited at Moffitt Cancer Center (MCC) and Georgetown Lombardi Comprehensive Cancer Center (LCCC). To identify specific factors impacting breast MRI utilization, we will sample women who are adherent to mammography screening (6-15% of whom have $\geq 20\%$ risk). Patients will self-report predisposing characteristics, enabling resources, perceived need for, and receipt of MRI in the past 12 months. Hypothesis: Lack of MRI uptake will be associated with predisposing characteristics related to lower preventive service use (less knowledge, higher fatalism), fewer enabling resources (less social support, higher cost/less insurance coverage), and less perceived need for screening breast MRI (lower perceived susceptibility, lack of provider recommendation for screening).

Aim 2: Confirm, refine, or expand our conceptual model of screening breast MRI utilization through in-depth semi-structured qualitative interviews with a subset of Aim 1 patients (N=30). Approach: We will purposively select information-rich cases from Aim 1 (N=30) for semi-structured qualitative interviews exploring factors impacting utilization of screening breast MRI. Research Question: Are there additional barriers/facilitators of MRI uptake not specified in the HSUM?

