Our long-term goal is to develop and test a community-based, multilevel intervention to increase screening breast MRI among high risk women. This study represents the first step in a new line of research, specifically focusing on developing interventions to facilitate personalized, risk-based cancer screening approaches. Successful completion of this study will provide an explanatory framework for screening breast MRI utilization. This explanatory framework will inform our program of research, ultimately leading to the development and testing of a community-based, multilevel intervention to increase screening breast MRI among high risk women. Given that early detection through screening MRI is a novel, important, and underutilized approach to prevention in high-risk populations, this research has potential for wide impact to improve guideline-concordant care and subsequent public health outcomes.

[figure not shown]
B. Background and Significance

Supplemental breast cancer (BC) screening modalities are recommended for women at elevated BC risk. In screening mammography populations, an estimated 6-15% of patients are at elevated BC risk (lifetime risk $\geq 20\%$)² based on personal health factors, family BC history, or pathogenic genetic mutations (e.g., *BRCA1/2*).²²⁻²⁵ Statistical models incorporating these risk factors are used to estimate lifetime BC risk,²⁶⁻²⁸ and national guidelines support their routine use to identify those with elevated BC risk.^{5,29} Once identified, the National Comprehensive Cancer Network (NCCN), American Cancer Society (ACS), and American College of Radiology (ACR) recommend that high risk women receive annual mammography and supplemental breast magnetic resonance imaging (MRI).^{4,5,30} In high risk women, MRI significantly increases BC detection (20-30 *additional* cancers per 1,000 women screened) compared to mammography alone.⁶ MRI has high sensitivity (71-100% v. 16-40% for mammography) in high-risk populations, and detects small and node-negative invasive tumors and higher grade DCIS that are less likely to contribute to over-diagnosis.

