However, few studies on BC screening have focused specifically on barriers/facilitators of breast MRI in high risk populations. Screening breast MRI is unique for three reasons. First, it is a supplemental procedure, to be done in addition to annual mammograms. Women who are adherent to mammography screening still have low rates of screening breast MRI.⁴⁵ Thus, the barriers to breast MRI are ones that do not prevent women from receiving mammograms. Second, screening breast MRI is only recommended for women with high BC risk. These women may differ significantly from the general population in terms of HSUM factors, including predisposing factors, enabling factors, and perceived need. Finally, the scant literature on screening breast MRI demonstrates unique features of the MRI procedure itself that may impact utilization, including medical contraindications, fewer MRI facilities, and significantly greater costs.^{10,18,19} Furthermore, existing studies are limited; they are retrospective in nature and include homogeneous populations.

This project is based on rigorous prior research demonstrating (a) established risk factors for BC,²²⁻²⁵ (b) a proven modality for screening this population (e.g., breast MRI),⁶ and (c) under-utilization of screening breast MRI in women at high BC risk.^{7,11} Thus, we propose a descriptive, cross-sectional, mixed-methods study of barriers to screening breast MRI utilization among high risk women. Guided by

the HSUM, we will conduct a comprehensive quantitative and qualitative assessment of barriers to MRI utilization. In Aim 1, community-based high risk women (N=300) will be surveyed regarding HSUM factors and breast MRI utilization. Results will identify patient-level HSUM factors significantly associated with screening outcomes. In Aim 2, a subset of Aim 1 patients (N=30), will complete semi-structured interviews to identify gaps in our theoretical conceptualization of breast MRI utilization. Successful completion of this study will provide an explanatory framework for screening breast MRI utilization. This explanatory framework will inform our program of research, ultimately leading to the development and testing of a community-based, multilevel intervention incorporating individual (e.g., education, motivational interviewing), provider (e.g., education, reminders/notifications), and/or systems-level (e.g., patient navigation, screening voucher) components.

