C.4.a Aim 1 Overview. The survey employed in this aim will be based on the HSUM and iteratively revised based on CAB feedback. Measures will be selected and adapted for relevance to MRI screening; potential measures are listed below (Section C.4.a.4). The Moffitt Cancer Center (MCC) Population Research, Interventions, and Measurement (PRISM) Core will assist with survey design and production. The PRISM Core has expertise in developing surveys that are acceptable and easy-to-understand, which subsequently enhances the quality of survey data.⁴⁹ The resulting survey will assess predisposing factors, enabling factors, perceived need, and health behaviors. The goal is to inform future intervention studies addressing patient barriers to screening breast MRI.

C.4.a.1 Aim 1 Inclusion/Exclusion Criteria. Biological females; able to speak/read English; within 2 years of last screening mammogram. Women will self-report *BRCA1/2* status; women with a pathogenic *BRCA1/2* mutation are eligible. Non-carriers, women with a variant of uncertain significance, and women with unknown carrier status will then be screened for lifetime BC risk using the National Cancer Institute (NCI) Breast Cancer Risk Assessment Tool (BCRAT).²⁶ For the proposed study, women with estimated lifetime risk $\geq 20\%$ will be eligible. We will exclude women with a prior diagnosis of BC.

The inclusion criterion of age will vary based on *BRCA1/2* status. For women with a pathogenic *BRCA1/2* mutation, women ages 25-85 will be eligible, as breast MRI screening is recommended to be initiated at age 25 for this population. For women without a pathogenic *BRCA1/2* mutation, women ages 35-85 will be eligible.

C.4.a.2 Aim 1 Ascertainment and Enrollment. To enroll 300 participants, we will use five different recruitment strategies.

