TDM to distribute the survey. We will use the following approach: (1) mailed packet including a cover letter, two copies of the informed consent form, paper survey, URL for the web-based survey, and postage paid return envelope; (2) 1st thank you/reminder postcard; (3) replacement survey; (4) 2nd thank you/reminder postcard; and (5) a final survey with a letter stating a final date for survey submission. Materials will be mailed every 2 weeks.

Upon completion, all survey respondents will receive a \$10 gift card.

C.4.a.4 Aim 1 Measures. Predisposing factors: Sociodemographics, medical contraindications for MRI, BC Awareness Scale,⁶⁰ Multidimensional Health Locus of Control Scale⁶¹ and Medical Outcomes Study 12-Item Short Form Health Survey (SF-12)⁶². Enabling factors: Medical Outcomes Study Social Support Survey,⁶³ cost/insurance factors (employment, income, insurance), site of care, access to on-site MRI, and travel time to site of care. Perceived need: Perceived susceptibility,⁶⁴ perceived norms,⁶⁵ provider recommendation for screening, and attitudes towards screening.⁴⁶ Health Behaviors: Patient-reported receipt of BC screening (mammogram, ultrasound, and MRI) and other BC risk management behaviors (chemoprevention, genetic counseling/testing) in the last 12 months.

C.4.a.5 Aim 1 Analytic Approach.

Data Management and Analysis: We will calculate descriptive statistics for predisposing factors, enabling factors, perceived need and health behaviors. We will use multivariable logistic regression to estimate odds ratios (ORs) for the relationships of the HSUM predictors with health behaviors. In the event that data is missing, we will use multiple imputation (with data assumed to be missing at random) to assess the robustness of results based on participants with complete data. We will account for site of recruitment (e.g., MCC or LCCC) in all analyses.

Sample Size: With N=300, we will have >80% power for multivariable logistic regression examining ORs at $\alpha=0.05$ (two-tailed). We can detect OR=1.8 when the predictor (X) is continuous and normally distributed, the probability of screening at the mean of X is 0.2, and the coefficient of determination between X and a continuous covariate (Z) is 0.05. When X and Z are binary with 50% and 25% prevalence, respectively, we will have 75% power to detect OR=2.5, when the probability of screening is 0.25 when X=0 and Z=0.

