Expected Outcomes: Upon completion of Aim 2, we expect to identify additional barriers/facilitators of MRI uptake that are not specified in the HSUM. This will allow us to refine the conceptual model in Aim 1.

C.4.c Integration of Findings. Qualitative and quantitative findings will be integrated during the post-hoc modification of the conceptual model. We will use the merging approach, which combines qualitative and quantitative data to compare and analyze.^{74,75} Data display tables will be constructed so that corresponding qualitative and quantitative data can be juxtaposed, discussed, compared, and interpreted.⁷⁶ This will allow the team to use the qualitative and quantitative findings to inform modifications of the conceptual model.

D. Human Subjects.

D.1 Risks to Human Subjects

D.1.a Human Subjects Involvement, Characteristics, and Design

Aim 1 involves a one-time survey of women at high risk (n=300) for breast cancer (BC). The survey will assess predisposing characteristics, enabling resources, perceived need for, and receipt of MRI in the past 12 months. Breast MRI referral and uptake will be the primary outcome measures investigated in Aim 1. The survey will be completed on paper or via internet (as preferred). We will also utilize minimal intensity, low resource effective strategies including thank you/reminder post cards. Materials will be mailed every 2 weeks. Surveys are estimated to take 30-45 minutes. Upon completion, survey respondents will receive a \$10 gift card.

To be eligible for Aim 1, participants must be: (a) biological females; (b) able to speak/read English or Spanish; (c) within 2 years of last screening mammogram; and (d) able to give informed consent. Women will self-report *BRCA1/2* carrier status; women with a pathogenic mutation in these genes are eligible. Non-carriers will then be screened for lifetime BC risk using the National Cancer Institute (NCI) Breast Cancer Risk Assessment Tool (BCRAT; <https://bcrisktool.cancer.gov/calculator.html>), an interactive web-based tool based on the Gail model²⁶; women with estimated lifetime risk $\geq 20\%$ are also eligible. We will exclude women with a personal history of BC.

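### Mammography entry window is 24 months but MRI is counted over 12: pre-specify a sensitivity analysis in women with a mammogram in the last 12 months

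*Combined protocol and SAP*

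**What the plan says.** The Aim 1 statement gives the sampling intent: "we will sample women who are adherent to mammography screening". Section B gives the reason. Women who attend mammography still have low MRI use, and the text concludes: "Thus, the barriers to breast MRI are ones that do not prevent women from receiving mammograms". Section B also reports that national bodies "recommend that high risk women receive annual mammography" together with supplemental MRI.

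The criterion that puts this into practice, in C.4.a.1, is "within 2 years of last screening mammogram". D.1.a repeats it with the same window, so it is not a slip in one place. The outcome has a shorter window: Aim 1 and D.1.a both refer to "receipt of MRI in the past 12 months".

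C.4.a.4 lists, under health behaviors, "Patient-reported receipt of BC screening (mammogram, ultrasound, and MRI", plus other risk management behaviors, all over the last 12 months. C.4.a.5 plans multivariable logistic regression of health behaviors on the HSUM predictors. The only adjustment it names is recruitment site. It gives no restriction, stratification or sensitivity analysis by time since last mammogram.

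**The concern.** The design separates MRI-specific barriers from general ones by holding mammography use constant. For a woman whose last screening mammogram was 12-24 months ago, it is not held constant over the period in which MRI is counted: she had no screening mammogram in that period. If such women also have fewer MRIs, any factor that makes them late for screening in general will be associated with lack of MRI in the pooled sample.

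The factors most exposed are the enabling ones. Section B says that social support, cost or insurance, and access to care predict breast screening generally, and the Aim 1 hypothesis names social support and cost/insurance as predictors of MRI uptake. C.4.a.5 expects to single out two to four leading factors and to use their effect sizes to power a later randomised trial. A general attendance factor labelled as MRI-specific would carry over into that intervention.

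**Working it through.** **1. Windows side by side.**

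| Element | Window | Where |
|---|---|---|
| Recommended mammography, as cited | annual | Section B |
| Mammogram for entry | 24 months | C.4.a.1, D.1.a |
| MRI outcome | 12 months | Aim 1, C.4.a.4, D.1.a |
| Mammogram item in survey | 12 months | C.4.a.4 |
| Use of mammogram timing in the MRI model | none named | C.4.a.5 |

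**2. Size of a spurious association.** The plan states no figure for this, so every input here is an assumption. Let f be the share of women at 12-24 months, m_L and m_C the MRI uptake in these and in the other women, and x_L and x_C the prevalence of a favourable factor X in the two groups. X is unrelated to MRI within each group. Then

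- P(MRI | X=1) = [(1−f)·x_C·m_C + f·x_L·m_L] / [(1−f)·x_C + f·x_L]
- P(MRI | X=0) is the same with 1−x_C and 1−x_L in place of x_C and x_L.

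*Low case* (f=0.15, m_L=0.08, m_C=0.30, x_L=0.35, x_C=0.50):
- X=1: (0.425×0.30 + 0.0525×0.08)/0.4775 = 0.1317/0.4775 = 0.276
- X=0: (0.425×0.30 + 0.0975×0.08)/0.5225 = 0.1353/0.5225 = 0.259
- OR = (0.2758/0.7242)/(0.2589/0.7411) = **1.09**

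*High case* (f=0.35, m_L=0.03, m_C=0.30, x_L=0.30, x_C=0.50):
- X=1: (0.325×0.30 + 0.105×0.03)/0.43 = 0.10065/0.43 = 0.234
- X=0: (0.325×0.30 + 0.245×0.03)/0.57 = 0.10485/0.57 = 0.184
- OR = (0.2341/0.7659)/(0.1839/0.8161) = **1.36**

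Overall MRI uptake is 26.7% and 20.6%, near the 0.20 and 0.25 used in C.4.a.5. If m_L = m_C, the OR is **1.00**.

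**3. A second grid.** X is held at 50% overall, its odds ratio with being at 12-24 months is 2-3, and MRI uptake is 25-30% against 5-10%. The spurious OR is 1.05-1.12 at f=10%, 1.10-1.25 at 20%, 1.14-1.38 at 30% and 1.17-1.50 at 40%.

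**4. Chance of a false positive.** With N=300 and the expected cell counts from step 2, SE(ln OR) is 0.261 and 0.287. So ln(OR)/SE is 0.33 and 1.06, and the chance of two-sided p<0.05 is about 6% and 19%, against 5% nominal.

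**5. Power of a restricted run.** First, the plan's own figures at N=300, two-sided 0.05.
- Continuous X: Φ(√[N·P(1−P)(1−R²)]·ln OR − 1.96), with P=0.2, R²=0.05, OR=1.8, gives Φ(3.97−1.96) = 97.8%. The plan states above 80%, which is true but loose.
- Binary X: two proportions, 0.25 against 0.4545 (OR 2.5), 150 per group, gives 96.3%. The plan states 75%, which does not reproduce. At N=150, the size in Table 1, the same formulas give 80.1% and 75.1%. That conflict is a separate matter.

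Keeping only women with a mammogram in the last 12 months:

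| Share excluded (assumed) | N left | OR 1.8, continuous | OR 2.5, binary |
|---|---|---|---|
| 10% | 270 | 96.5% | 94.5% |
| 20% | 240 | 94.4% | 91.8% |
| 30% | 210 | 91.3% | 87.9% |
| 40% | 180 | 86.7% | 82.5% |

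This holds for 300 enrolled. With 150, power starts at the 80.1% and 75.1% above and falls from there.

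**The case against.** The case for leaving the plan alone has several parts.

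- **Adherence is not defined.** C.4.a.1 sets an entry rule and never says that two years means adherent. That is correct; a reader might infer such a definition, but the text does not give one. Still, no other criterion carries out the stated sampling intent.
- **Late is not the same as unscreened.** A reader might infer that women at 12-24 months had no breast imaging in the outcome window. The documents do not support this: ultrasound and MRI are asked about separately, and the scenarios above give these women some MRI. Only the absence of a screening mammogram follows.
- **Just past 12 months may be on schedule.** C.4.a.2 recruits some women in clinics before a scheduled visit, and paper surveys come back by mail. A 12-month yes/no item will class some women on an annual schedule as late. This stands, and is a reason to keep the restricted run as a sensitivity analysis.
- **Mammogram receipt is already a listed health behavior.** Read plainly, C.4.a.5 would regress it on the same predictors, and comparing the two sets of odds ratios would help. But the plan does not state that comparison, and D.1.a names MRI referral and uptake as the primary outcomes.
- **Adjustment changes the question.** A reader might conclude that mammogram receipt belongs as a covariate in every MRI model. It is a co-outcome over the same window and may itself result from insurance, travel or support. Adjusting would remove effects that act through attendance, whereas Aim 1 asks what influences MRI use overall. This objection stands. The restricted run also conditions on mammography, but it is labelled as secondary, follows the design's own logic, and leaves the main odds ratios with their planned meaning.

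**Conclusion.** The mismatch is in the documents: a sample meant to hold mammography constant admits women with no screening mammogram in the 12 months over which MRI is counted, and the analysis does not use mammogram timing. The consequence is conditional. It requires that MRI uptake is lower in these women and that the factor is related to being late. The documents give no figure for either, nor for the share of such women.

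Under the assumed ranges the spurious odds ratio is 1.09-1.36, or 1.05-1.50 on the wider grid, and 1.00 if uptake does not differ. All of these lie below the design odds ratios of 1.8 and 2.5. A general attendance factor therefore may appear as MRI-specific; the documents do not support saying that it will. Nor do they show the entry window to be wrong, since a two-year window can be a reasonable recruitment choice. This is a small to moderate weakness in interpretation with a cheap remedy.

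**What to change.** Keep the 2-year entry window and the planned main model. In C.4.a.5, pre-specify one sensitivity analysis that repeats the main HSUM odds ratios for MRI in women who report a mammogram in the last 12 months. State that a factor will be called MRI-specific only if its estimate is similar in that group, and say in advance what counts as similar, judged on the odds ratio and its interval and not on whether significance is kept. Do not add mammogram receipt as a covariate in every MRI model.

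C.4.a describes its measures as potential, so confirm that the 12-month mammogram item stays in the final survey.

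The cost is one extra run on data already planned, with no change to eligibility or recruitment. The restricted run has fewer women and wider intervals, and leaves out some on-schedule women just past 12 months. With 300 enrolled, power at the design odds ratios stays above 80% even if 40% of women are excluded.

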For Aim 2, participants who provide contact information at the end of the Aim 1 survey will be randomly selected and invited to interview until we have achieved our desired sample size (N=30). Participants will be contacted using their preferred method. Upon confirmation of interest, participants will be sent two copies of the informed consent, one of which will be signed and returned to MCC or LCCC (depending on site of recruitment). Consenting participants will be scheduled for an individual interview via telephone.

Sources of research material (to be used for research purposes only) include the following:

- a) Self-report inventories assessing: sociodemographic, clinical, and cultural characteristics; BC awareness, psychological well-being, perceived social support, perceived BC susceptibility, perceived norms, provider recommendation for BC screening, attitudes towards BC screening, receipt of BC screening in the last 12 months, and other BC risk management behaviors in the last 12 months.
- b) Audio-tapes and transcripts of interviews.

There are no physical risks to the participant posed by this study, and no adverse events are anticipated. Participation in this project will require the investment of time in responding to interviews and survey questionnaires. This is a minimal risk study. We are using standard interview and survey techniques. Study participants will not encounter risk greater than those ordinarily encountered in daily life, including clinical encounters in the primary care and BC screening settings. These minimal risks are described in detail below.

- a) Confidentiality and loss of privacy. Subjects may provide personal information about themselves during the in-depth interviews, as well as on screening or demographic questionnaires. Disclosure of personal or health-related information may affect a participant's employability or reputation.
- b) Psychological distress and cancer risk data, which is sensitive and personal information, will be collected in this study. Participants may feel embarrassed or uncomfortable with disclosing such information.

D.2 Adequacy of Protection Against Risks

D.2.a Informed Consent

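### Genetic counseling/testing is scored only over the last 12 months, so women tested earlier fall in the comparison group with women never tested, and the odds ratios for this secondary behavior mislead as a measure of barriers

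*Combined protocol and SAP*

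**What the plan says.** C.4.a.4 (Aim 1 Measures) defines the health behaviors as patient-reported mammogram, ultrasound and MRI, plus "other BC risk management behaviors (chemoprevention, genetic counseling/testing) in the last 12 months". D.1.b repeats the same look-back in its list of self-report inventories: "and other BC risk management behaviors in the last 12 months".

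C.4.a.5 (Aim 1 Analytic Approach) makes these behaviors the outcomes. Multivariable logistic regression will "estimate odds ratios (ORs) for the relationships of the HSUM predictors with health behaviors".

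C.4.a.1 (Inclusion/Exclusion Criteria) lets in women who already know their result: "Women will self-report *BRCA1/2* status; women with a pathogenic *BRCA1/2* mutation are eligible". It continues: "Non-carriers, women with a variant of uncertain significance, and women with unknown carrier status will then be screened for lifetime BC risk". There is no condition on the date of the test. C.4.a.2 adds recruitment through the e-mail list of an advocacy group for hereditary cancer, with a high-risk breast clinic as a fallback source.

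The documents contain no ever-tested item, no restriction of this model to women still untested at the start of the window, and no rule for coding women tested earlier.

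**The concern.** A 12-month look-back suits imaging that is recommended every year. It suits genetic testing less well, because a woman who already has a result has little reason to test again. A woman who reports being a carrier, or having a variant of uncertain significance, has been tested. If that was more than a year ago, and she had no counseling since, the definition scores her *no* although her own screening answer shows that she used the service.

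The *no* group then holds two kinds of women: those who have not used the service, and those who used it and were finished with it. The Health Services Utilization Model (HSUM) is meant to explain why a service is or is not used, and the second kind is not a sensible comparison group for that. These women may also differ in awareness and perceived susceptibility, so mixing them in need not be neutral. At stake is the reading of one secondary set of odds ratios.

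**Working it through.** **No figure to reproduce.** The documents give no prevalence, test timing, odds ratio or power figure for genetic counseling/testing. The power statement in C.4.a.5 concerns screening. All numerical inputs below are therefore assumptions, apart from N = 300.

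**Step 1: who is scored *no* under the written definition.**

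| Woman at entry | Used the service? | Scored under C.4.a.4 |
|---|---|---|
| Status unknown, never tested or counseled | No | *no* |
| Tested within the last 12 months | Yes | *yes* |
| Carrier, tested non-carrier or variant of uncertain significance; tested earlier, no counseling since | Yes | *no* |
| The same, but counseled in the last 12 months | Yes | *yes* |

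The third row is the problem.

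**Step 2: share of tested women outside the window.** If test dates are spread evenly over the past T years, the share is 1 − 1/T: 67% for T = 3, 80% for T = 5 and 90% for T = 10. If 100 of 300 women were ever tested, T = 5 leaves 100 × 0.20 = 20 events and puts 80 tested women in the *no* group.

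**Step 3: timing unrelated to the predictor.** Take a binary predictor with 50% prevalence, and ever-tested proportions p1 = 0.41 and p0 = 0.258 (mean about 0.33).

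- Ever-tested: (0.41/0.59) / (0.258/0.742) = 0.695/0.348 = 2.0.
- With a fraction s of tested women inside the window, the 12-month odds ratio is [s·p1/(1 − s·p1)] / [s·p0/(1 − s·p0)].
- s = 1/3: (0.137/0.863) / (0.086/0.914) = 1.68.
- s = 0.2: (0.082/0.918) / (0.0516/0.9484) = 0.0893/0.0544 = 1.64.
- s = 0.1: (0.041/0.959) / (0.0258/0.9742) = 1.61.

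As s falls to zero, the ratio tends to p1/p0 = 0.41/0.258 = 1.59. On these inputs, even timing alone cannot push the odds ratio to 1.

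**Step 4: timing that differs by predictor level.** Keep p1 and p0.

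- 15% of tested women with the predictor and 30% of those without it inside the window: (0.0615/0.9385) / (0.0774/0.9226) = 0.0655/0.0839 = 0.78.
- The reverse: (0.123/0.877) / (0.0387/0.9613) = 0.140/0.0403 = 3.5.

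A wider grid took ever-tested proportions of 25% or 50% without the predictor, true odds ratios of 1.8 or 2.5, and earlier-tested shares of 50% v 80% or 70% v 90%, either way round. The 12-month odds ratio ran from 0.39 to 6.16. This shows that the direction is not predictable; it is not an estimate for this study.

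**Step 5: effect of restricting to women not tested before the window.** The odds in each group become s·p/(1 − p). With equal s, the ratio is (0.082/0.59) / (0.0516/0.742) = 0.1390/0.0695 = 2.0, so the ever-tested value is recovered. With unequal s, it is 2.0 × s1/s0 (for 15% v 30%, 1.0). That is not the ever-tested odds ratio, but it has a clear meaning: uptake in the last year among women not yet tested. In the T = 5 example, 300 − 80 = 220 women and the same 20 events remain.

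**The case against.** **The odds ratios are not wrong.** The stated outcome is counseling/testing in the last 12 months, and the regression estimates that correctly. A reader might infer an analysis error, but the documents do not support this: nowhere do they present these odds ratios as describing ever-use. This stands. The weakness is in what the contrast can tell us about barriers.

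**The effect on the study is limited.** D.1.a names MRI referral and uptake as the primary outcomes. The Aim 1 hypothesis, Table 1, the power statement, and the Aim 2 grouping in C.4.b.1 and Table 3 all concern MRI or screening. This stands too.

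**The coding is inferred.** The overview in C.4.a calls the measures provisional, the questionnaire is not in the documents, and a carrier counseled this year could still be *yes*. This is fair. But two sections state the window, and nothing provides another coding.

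**Screening status already reveals past testing.** This is partly right. Known status with a *no* answer points to an earlier test, so many of these women could be found. The plan does not commit to doing so. Status carries no date, does not show earlier counseling alone, and cannot separate an earlier-tested woman who was counseled recently from one tested recently.

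**Ever/never has its own flaw.** Predictors are measured once, at the survey. A result received years ago may have changed perceived susceptibility, so the association could run backwards. This stands, and it is why ever/never should not replace the 12-month outcome as the main analysis.

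**Conclusion.** The point holds as a limitation of a secondary outcome. Followed as written, the plan places already-tested women alongside never-tested women, and nothing elsewhere in the documents corrects this. The resulting odds ratios describe recent testing in a mixed group and should not be read as showing what keeps women from using the service.

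The size cannot be determined. If 80% of tested women were tested earlier, equally across predictor levels, an odds ratio of 2.0 becomes about 1.6. If timing differs by predictor, it could move either way, including across 1.

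Two stronger readings are not supported. A reader might infer that the recruitment sources guarantee many earlier-tested women; they make such women likely, but the documents give no count of carriers and describe the e-mail list only by its members' interest in hereditary cancer. A reader might also infer that the findings on MRI are compromised; neither the MRI outcomes nor the Aim 2 grouping uses this variable.

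**What to change.** - **C.4.a.4 and D.1.b:** ask separately whether the woman ever had genetic counseling and ever had genetic testing, with the year of each. Keep an item on whether each fell in the last 12 months, because a year alone may not settle that.
- **C.4.a.5:** for this behavior, restrict the 12-month model to women not tested before the window. State how a woman counseled but not tested before the window is handled.
- **C.4.a.5:** report ever/never as a sensitivity analysis, with a note that a past result may itself change perceived susceptibility.
- **Consistency check:** compare the answers with the BRCA1/2 status from screening. Do not exclude carriers alone: that drops only women known to have been tested, so it selects on the outcome, and it leaves tested non-carriers and women with a variant of uncertain significance in place.

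The look-back for the other behaviors can stay.

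The cost is one or two survey items, a few sentences in C.4.a.5, some recall error over a longer period, and a smaller sample for this secondary model (220 of 300 in the T = 5 illustration, with no loss of events there). The items need to be in place before the survey is fielded, since screening status alone cannot supply the dates later.
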